Potential Risks associated with EDWARDS INTUITY Aortic Valves and Delivery Systems may be found in the respective IFU. Based on a review of scientific literature, preliminary animal studies, risk analysis and a Failure Modes and Effects Analysis (FMEA) potential risks associated with the use of the EDWARDS INTUITY Aortic Valves may include:

- Loss of frame structural integrity resulting in damage to aortic wall or aortic annulus
- Delivery system impingement resulting in mitral chordae trauma or damage
- Frame damage or flaring resulting in a reduction of effective orifice area
- Hemolysis
- Frame expansion resulting in conduction interruptions or disturbances (i.e. arrhythmia)
- Frame expansion resulting in mitral valve impingement or abrasion with or without mitral regurgitation
- Insufficient frame expansion/suturing resulting in paravalvular leak requiring intervention or reoperation to resolve
- Device malpositioning resulting in ostial blockage
- Device embolization into the aorta/ventricular due to suture failure

Some or all of these risks could require a need for reoperation or explant, and may lead to permanent disability or death.

There may be other risks that are unknown at this time. All safety events will be collected and reviewed throughout the entire investigation and follow-up period. Investigators will be notified of any additional risks identified that could affect the health, safety or welfare of the investigation subjects.

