5 ENDPOINTS

5.1 SAFETY ENDPOINTS

The following primary safety endpoints will be assessed throughout each subject's participation in the investigation:

- Study valve-related mortality
- Thromboembolic events
- Study valve thrombosis
- Major bleeding events
- Study valve paravalvular leakage
- Study valve-related endocarditis

In addition, the following safety endpoints will also be assessed throughout each subject's participation in the investigation:

- All-cause mortality
- Study valve structural valve deterioration
- Hemolysis
- Study valve-related reoperation
- Study valve explant
- All adverse events

⁵ This may include subjects who expired or had the valve explanted prior to 1 month.

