5.3 OTHER DATA

The following data also will be collected:

- EQ-5D Quality of Life questionnaire at baseline, 3-months and 1-year only,
- Blood data (White Blood Cell Count, Red Blood Cell Count, Hemoglobin, Hematocrit, Haptoglobin, Reticulocytes, Platelet Count, Serum Lactate Dehydrogenase) at baseline, 3-months, 1- and 5-years only,
- New onset or worsening of conduction disturbances.

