11.2.1 Adverse event

An adverse event (AE) is defined as any untoward medical occurrence, unintended disease or injury, or untoward clinical signs (including abnormal laboratory findings) in subjects, users or other persons, whether or not related to the investigational medical device.

NOTE 1: This definition includes events related to the investigational medical device or the comparator.

NOTE 2: This definition includes events related to the procedures involved.

NOTE 3: For users or other persons, this definition is restricted to events related to investigational medical devices.

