12.3 PHASE I ANALYSIS

Phase I consists of the first 10 subjects enrolled to the investigation.

The following primary safety endpoints will be summarized by counts and percentages based on 30-day follow-up:

- study valve-related mortality,
- thromboembolic events,
- study valve thrombosis,
- major bleeding events,
- study valve paravalvular leakage, and
- study valve endocarditis.

In addition, the following safety endpoints will also be summarized by counts and percentages based on 30-day follow-up:

- all-cause mortality,
- study valve structural valve deterioration,
- hemolysis,
- study valve-related reoperation,
- study valve explantation, and
- all adverse events.

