12.4.2 SAFETY ANALYSIS

For reporting purposes, the percent of subjects who experience an early adverse event within 30 days of implant for the events listed in the primary safety endpoints will be summarized. Linearized rates will be used to summarize adverse events for the late (>30 days) post-operative period for the events listed in the primary safety endpoints. The linearized rates will be reported as the number of events occurring after the early post-operative period per year of subject survival.

Actuarial analysis according to Kaplan-Meier will be used to estimate probability of freedom from each adverse event listed in the primary safety endpoint.

The percentages for the early events and linearized rates for the late events will also be calculated for the other complications.

Blood data (red blood count, white blood count, hematocrit, hemoglobin, platelet count, serum lactate dehydrogenase, haptoglobin, and reticulocytes) will be collected preoperatively, at 6-months, 1-years, and 5-years post implant. Data will be reported as the percent of subjects with results within the normal ranges at each time interval.

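### Section 12.4.2 summarizes the blood parameters only as percent within normal range, so within-subject change and direction are lost and laboratory signs of new, unreported hemolysis can be masked in that table

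*Combined protocol and SAP*

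**What the plan says.** **Blood data.** Section 12.4.2 names red and white cell counts, hematocrit, hemoglobin, platelets, LDH, haptoglobin and reticulocytes. Its whole plan for them is: "Data will be reported as the percent of subjects with results within the normal ranges at each time interval". It states that the data "will be collected preoperatively, at 6-months, 1-years, and 5-years post implant". Section 5.3 lists the same parameters under other data, but "at baseline, 3-months, 1- and 5-years only".

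**Hemolysis as an event.** This is handled separately. The second list in Section 5.1, which opens "In addition, the following safety endpoints will also be assessed throughout each" subject's time in the study, includes hemolysis. For Phase I, Section 12.3 puts hemolysis in the list for which "the following safety endpoints will also be summarized by counts and percentages based on 30-day follow-up". For Phase II, Section 12.4.2 adds: "The percentages for the early events and linearized rates for the late events will also be calculated for the other complications". The adverse event definition in Section 11.2.1 covers "untoward clinical signs (including abnormal laboratory findings").

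**Echo data, for contrast.** Section 12.4.3 plans descriptive change from baseline for the continuous echo variables, and paired tests at one year. Nothing similar is planned for blood data.

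**The concern.** Hemolysis is a safety endpoint. It is also a bullet of its own in Section 3.1, in the list of potential risks of this valve, and the same section names it as a risk of stented bioprostheses generally. The stated purpose is to confirm that adding the expandable frame does no harm, so laboratory signs of red-cell destruction after implant bear directly on the question.

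Event reporting depends on someone recognizing hemolysis and recording it. The visible text gives no laboratory criterion for the hemolysis endpoint; Section 11 refers event codes to the eCRF synopsis. The 1-month evaluation schedules no blood studies in either phase (Section 9.4.3, Tables 5 and 6). The later scheduled blood draws are therefore the systematic check on hemolysis that nobody reported as an event.

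A group percentage within range is a weak form of that check. It does not show which subjects changed, and it counts values above and below the range alike.

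**Working it through.** The documents give no figure for the percent normal, and no test, alpha or power for blood data, so there is no stated number to reproduce. The check asks what the planned table can and cannot show.

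**Inputs**
- N = 10 + 340 = 350, the combined enrollment in Section 4.2. Complete data are assumed. The real denominator would be smaller, for example because Section 9.6 stops routine blood tests after discharge in subjects whose device was removed or explanted.
- p0 and p1, the percent normal at baseline and at follow-up, are assumptions.

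**1. What two group percentages say about new abnormality.** The share of all subjects who go from normal to abnormal lies between max(0, p0 − p1) and min(p0, 1 − p1).

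| Assumed p0 / p1 | Newly abnormal, share | Newly abnormal, of 350 |
|---|---|---|
| 90% / 90% | 0 to 10% | 0 to 35 |
| 80% / 80% | 0 to 20% | 0 to 70 |
| 70% / 70% | 0 to 30% | 0 to 105 |

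An unchanged percentage does not tell no change from substantial two-way movement.

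**2. How much offset masking needs.** Take 80% normal at baseline: 0.80 × 350 = 280 normal and 70 abnormal. Let 10% of the normal subjects turn abnormal: 0.10 × 280 = 28.
- If nobody normalizes, the percent normal becomes (280 − 28)/350 = 252/350 = 72%. The table moves by 8 points.
- To hide this completely, 28 of the 70 who were abnormal before surgery (40%) must become normal.

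Any smaller offset hides it in part.

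**3. Direction.** Assume haptoglobin goes from 5% low and 15% high to 15% low and 5% high. The percent normal is 100 − 5 − 15 = 80% before and 100 − 15 − 5 = 80% after. The table is unchanged, while (0.15 − 0.05) × 350 = 35 more subjects are low.

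**4. Are the visits of the table defined?** Side by side:
- Section 12.4.2: first post-implant draw at 6 months.
- Section 5.3: first post-implant draw at 3 months.
- Section 9.4.3, Table 4: no 6-month visit.
- Section 9.4.3, Table 7: blood studies listed for the 3-month and the annual visits, without the restriction in Section 5.3.

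These do not agree, so a baseline-by-visit table cannot yet be laid out. The difference also bears on Section 2.2.1, where the DMC judges Phase II on 3-month data: a first draw at 6 months would come after that time point.

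**The case against.** The strongest reply is that hemolysis is already covered. A reader might infer that hemolysis itself is reduced to a percent-normal figure and could go unseen in the trial. The documents do not support that. Hemolysis is its own endpoint, counted at 30 days in Phase I. In Phase II it is most naturally included in the complications that receive early percentages and late linearized rates, although that sentence does not itemize them. Abnormal laboratory findings can be adverse events, Section 10.2 requires notes on abnormal results, and an independent DMC and CEC are planned. This stands, and it confines the point to one descriptive laboratory table, mainly for changes never reported as events.

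A reader might also infer that baseline is ignored. It is not: the pre-operative draw is one of the tabulated time points. What is missing is the pairing within subjects.

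Third, masking needs offsetting change, and without it the percentage falls visibly. This also stands, as step 2 shows. Some offset is possible wherever some subjects are abnormal before surgery, but the documents do not say how many are.

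A reader might want to put a fixed figure on the information lost by a yes/no cut. The usual efficiency formula is for a single one-sided cut of a roughly normal variable. The plan uses a two-sided range, nothing in the documents supports normality for these analytes, and no test is planned, so no such figure is offered.

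Finally, nothing in Section 12.4.2 forbids extra tables. That is true, but tables specified in advance are more credible than tables chosen after the data are seen.

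**Conclusion.** The point holds for the blood parameters, not for the hemolysis endpoint. As planned, the laboratory table cannot show within-subject change or the direction of abnormality. Laboratory signs of new hemolysis not reported as an adverse event can be masked there when other subjects normalize or deviate the opposite way.

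The size depends on percentages that the documents do not give. With an assumed 80% normal at both times and complete data on 350, the table is compatible with 0 to 70 newly abnormal subjects; over assumed values from 90% to 70%, the upper end runs from 35 to 105. These are limits of what the table leaves open, not estimates of what will happen.

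No stated test or success criterion uses the percent-normal figure. This is a minor improvement in reporting, worth making because the paired data are already collected and the plan already uses change from baseline for echo.

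**What to change.** In Section 12.4.2:
1. Reconcile the blood-draw schedule across Sections 12.4.2 and 5.3 and Tables 4 and 7 of Section 9.4.3, so that the visits in the table are defined.
2. For each analyte, add a baseline-by-visit shift table (low, normal, high) and the median paired change from baseline, with the number of subjects who have both values. The percent within range can stay.
3. For LDH, haptoglobin, reticulocytes and hemoglobin, report the percent newly abnormal in the hemolytic direction among subjects normal at baseline, with exact 95% limits. State the direction for each analyte in advance (taken here as high for LDH and reticulocytes, low for haptoglobin and hemoglobin).
4. State the laboratory criterion for the hemolysis endpoint, or point to the document that holds it.

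The cost is one set of standard tables and a few sentences of text. The tables need no new visits, samples or subjects.

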12.4.3 PERFORMANCE ANALYSIS

The device technical success and procedure success will be summarized by counts and percentages.

Subjects will be analyzed according to the NYHA classification preoperatively, at 3 months and annually post implant for 5 years. The distribution (numbers of subjects and percentages) in the various NYHA classes will be tabulated at each follow-up interval.

Echocardiography data will be obtained preoperatively, at discharge (or 10-days post implant, whichever occurs first), at 6-months and at 1, 3, and 5 year follow-ups. Descriptive statistics for the continuous echo variables and change from baseline (e.g. mean, standard deviation, and range) will be categorized by time interval and size. Regurgitation data will be summarized using frequency at each severity level.

Improvement in regurgitation at one year will be analyzed via the Wilcoxon Signed-Rank test. Change at one year from baseline for all other hemodynamic outcomes will be analyzed using paired *t*-tests.

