5.2 PERFORMANCE ENDPOINTS

The following performance endpoint will be assessed when the investigation procedure is performed:

 Device technical success (successful delivery and deployment of one bioprosthesis with one delivery system)

The following performance endpoint will be determined when the subject is discharged from the hospital or 10 days post implant, whichever occurs first:

 Procedure success defined as device technical success followed by the absence of adverse events requiring device reoperation, requiring implantation of permanent pacemaker (with baseline sinus rhythm and no other conduction issues), or subject death

The following performance endpoints will be assessed at each scheduled follow-up visit:

- Improvement in NYHA functional class
- Hemodynamic performance (mean gradient, effective orifice area, regurgitation by echocardiogram).

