12.4 PHASE II ANALYSIS

12.4.1 ANALYSIS POPULATION

The primary safety analysis will include all the enrolled subjects including those enrolled in Phase I. The performance analysis will include the subjects who survived at least 30 days post implant.

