12.4.4 MISSING DATA

All statistical tests on the performance endpoints will be performed using only those subjects with available data required for endpoint analysis. No missing value imputation will be performed.

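### Improvement in NYHA class is a named performance endpoint, but the planned class tables never estimate it and cannot yield it

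*Combined protocol and SAP*

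**What the plan says.** Section 5.2 lists "Improvement in NYHA functional class" among the performance endpoints assessed at follow-up visits; the synopsis does the same. Neither says what counts as improvement.

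Section 12.4.3 gives the NYHA analysis in two sentences: "Subjects will be analyzed according to the NYHA classification preoperatively, at 3 months and annually post implant for 5 years", and "The distribution (numbers of subjects and percentages) in the various NYHA classes will be tabulated at each follow-up interval". No within-subject comparison, estimate or interval is planned.

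The same section does plan change for the echocardiographic outcomes:

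- "Descriptive statistics for the continuous echo variables and change from baseline" are to be presented by time interval and valve size.
- "Improvement in regurgitation at one year will be analyzed via the Wilcoxon Signed-Rank test".
- The remaining hemodynamic outcomes are to have their one-year change tested by paired t-test.

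NYHA class is neither an echo variable nor a hemodynamic outcome, so none of these covers it.

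On who is counted, Section 12.4.1 says: "The performance analysis will include the subjects who survived at least 30 days post implant". Section 12.4.4 rules out imputation. Sections 9.7 and 9.8 end follow-up at death, at withdrawal, or after two consecutive missed visits. No denominator is given for the NYHA table, and no row for subjects who have died or were not seen.

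**The concern.** The endpoint is a change from each subject's own baseline, whereas the analysis is a series of snapshots. A snapshot can stay the same while some subjects improve and as many worsen, and it can shift because the set of subjects in it has changed. Followed exactly, the plan produces no figure for the endpoint it names.

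According to Section 2.2, the results will support a CE Marking application and other registrations. Any later statement on how many subjects improved would need a definition and a denominator chosen after the data were seen.

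**Working it through.** The documents give no NYHA effect, baseline distribution or death rate by class, so there is no planned figure to reproduce. Step 1 is reading alone. Every distribution and loss rate in steps 2 to 4 is an assumption made for illustration.

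**1. Endpoint against analysis**

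| Outcome | Planned summary | Within-subject change? |
|---|---|---|
| Continuous echo variables | Descriptive statistics and change from baseline | Yes |
| Regurgitation | Frequencies; Wilcoxon signed-rank test at 1 year | Yes |
| Other hemodynamic outcomes | Paired t-test at 1 year | Yes |
| NYHA class | Number and percent per class at each interval | No |

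**2. Can improvement be recovered from the tables?** Assume complete data and a baseline I/II/III/IV of 5/40/50/5%. The bounds below come from linear programming over all joint distributions with the given margins.

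- *Follow-up also 5/40/50/5%.* Improved: 0% to 50%. Worsened: 0% to 50%. One simple case: 40% move from III to II and 40% from II to III. Class II is then 40 − 40 + 40 = 40% and class III is 50 − 40 + 40 = 50%. The tables are identical, yet 40% improved and 40% worsened.
- *Follow-up 55/35/9/1%.* Improved: 50% to 95%. Worsened: 0% to 15%. The lower limit for improved is 55 − 5 = 50%, because at most 5% can have stayed in class I. The upper limit is 100 − 5 = 95%, because those starting in class I cannot improve.

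**3. Can losses alone move the tables?** Let nobody change class. With baseline share p_k and loss d_k in class k, the observed share is p_k(1 − d_k) / Σ p_j(1 − d_j). Assume a baseline of 10/40/40/10%, so class III/IV is 50%.

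| Assumed mortality I/II/III/IV | Overall mortality | Class III/IV among those seen |
|---|---|---|
| 3/6/12/30% | 10.5% | (0.40 × 0.88 + 0.10 × 0.70) / 0.895 = 47.2% |
| 5/10/20/50% | 17.5% | (0.40 × 0.80 + 0.10 × 0.50) / 0.825 = 44.8% |
| Equal in all classes | any | 50.0%, since 1 − d cancels |

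A second set of assumptions shows how this depends on time. The baseline is 5/40/50/5%, so class I/II is 45.0%.

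- *1 year, losses 2/3/6/15%:* class I/II among those seen is 0.437 / 0.9495 = 46.0%, a drift of 1.0 point.
- *5 years, losses 12/16/24/40%:* 0.380 / 0.790 = 48.1%, a drift of 3.1 points.
- *5 years, losses 10/15/35/60%:* 0.385 / 0.730 = 52.7%, a drift of 7.7 points.

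In the two 5-year cases the share of all subjects who are still followed and in class I/II falls to 38.0% and 38.5%, while the tabulated share rises.

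**4. Would a paired estimate be precise enough?** If 240 of 300 paired subjects improved, the exact 95% limits would be 75.0% to 84.4%. By normal approximation, 1.96 × √(x(1 − x)/n) gives half-widths of 4.8 to 5.2 points with n = 350 and 5.4 to 5.9 points with n = 280, for true shares x of 70% and 50%. The planned 350 subjects are enough.

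**The case against.** The strongest reply is that little depends on this endpoint. It is one of several performance endpoints and has no hypothesis, margin or success rule. Under Section 2.2.1, Phase II succeeds on the Data Monitoring Committee's safety judgement from 3-month data. Deaths are not hidden either: all-cause mortality is a safety endpoint in Section 5.1. Preoperative class is also analysed, so a reader can see the net shift next to mortality. All of this stands, and it limits the severity. It does not supply the missing figure, since neither the net shift nor the mortality rate shows how many subjects improved or worsened.

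Three stronger readings are tempting, and the documents do not support them.

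- *That deaths of sicker patients will make the tables look better.* This needs higher loss in worse classes, and no section gives loss by class. Even a tenfold mortality gradient moved the class III/IV share by only 2.8 or 5.2 points (50.0 − 47.2 and 50.0 − 44.8). Drift of this size would not explain a large post-operative shift by itself. The 30-day-survivor rule matters too. If the preoperative table uses that population, early deaths leave both tables and cannot create drift; if it uses all enrolled subjects, they can add to it. The text does not say which applies.
- *That the plan prescribes an available-case NYHA analysis.* The sentence in Section 12.4.4, "All statistical tests on the performance endpoints will be performed using only those subjects with available data required for endpoint analysis", concerns tests, and NYHA has none. That only subjects with an assessment appear in the table is an inference. It is a reasonable one, because nothing is imputed and no other category exists.
- *That the trial expects 13% mortality at three years.* Sections 2.1 and 3.3 cite 87% three-year survival in one published series of operated patients. That is background, not a planning assumption, and it says nothing about mortality by NYHA class.

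**Conclusion.** The main point holds on the text alone: the NYHA endpoint in Section 5.2 has no definition and no matching within-subject summary in Section 12.4.3, and the planned tables cannot supply one even with complete data.

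The second point is conditional. The tables can drift toward better classes if losses are higher in worse classes. Under the assumptions above, the drift is about 3 to 5 points in the class III/IV example, about 1 point at 1 year, about 3 to 8 points at 5 years, and zero when losses are equal across classes. These figures illustrate the mechanism and do not predict this trial's result.

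Severity is minor to moderate. This is a free improvement to the reporting of one performance endpoint and does not threaten the study's stated success criteria.

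**What to change.** In Section 12.4.3, keep the distribution table and add the following:

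- A definition of improvement, such as at least one class better than the subject's own preoperative class.
- A shift table of baseline class by class at 3 months and at each annual visit, with the number and percent improved, unchanged and worsened, and exact 95% limits.
- Death and missing or lost to follow-up as separate categories, so that each table adds up to a fixed, stated denominator.
- A statement of that denominator: either all enrolled subjects, which means departing from Section 12.4.1 for this endpoint, or 30-day survivors with the early deaths reported alongside.
- A note that subjects in class I at baseline cannot improve, with their number shown.

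The cost is one extra table and a few sentences. NYHA class is already collected at baseline (Sections 9.1 and 9.1.3) and at the 3-month and annual visits (Table 7). No further subjects, visits or data are needed.
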